4.2.1 Inclusion Criteria

1. Adult (≥18 years of age) able to provide signed, written informed consent.
2. Stable heart failure (NYHA II-IV) on maximally-tolerated background therapy (as determined by the site Principle Investigator) for at least 2 weeks prior to randomization.
3. Able and willing to perform a 6MWT at the time of randomization.
4. Reduced left ventricular ejection fraction. Assessment must be performed at least 12 weeks after major cardiac surgical intervention including coronary artery bypass graft (CABG), valvular repair/replacement, or cardiac resynchronization therapy (CRT) device implantation.
 - a. Left ventricular ejection fraction ≤40% obtained during the screening visit OR either of the following
 - i. Historical value of ejection fraction ≤40% within 24 months of screening visit

- ii. Historical value of ejection fraction $\leq 30\%$ within 36 months of screening visit
5. Hemoglobin >9.0 g/dL and <13.5 g/dL (females) or <15.0 g/dL (males) within 28 days of randomization.
 6. Serum ferritin <100 ng/mL or 100 to 300 ng/mL with TSAT $<20\%$. Patients with screening ferritin <15 ng/mL must have documentation of an appropriate evaluation, as determined by the Principle Investigator, within 3 months of screening and prior to randomization.
 7. Either documented hospitalization for heart failure within 12 months of enrollment or elevated N-terminal-pro-brain natriuretic peptide (NT-proBNP) within 90 days of randomization:
 - a. For patients in normal sinus rhythm: N-terminal-pro-brain natriuretic peptide (NT-proBNP) >600 pg/mL (or BNP >200 pg/mL)
 - b. For patients in atrial fibrillation: NT-proBNP >1000 pg/mL (or BNP >400 pg/mL)

NOTE: NT-proBNP must be used to confirm eligibility for patients taking sacubitril/valsartan.

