6.2 Screening Phase (Day -28 to Day 0)

6.2.1 Screening Visit

Each participant who has signed the informed consent and qualifies for inclusion will undergo the following clinical evaluations to confirm eligibility for the study (all procedures to be performed by blinded study personnel):

- Demographic and medical history including NYHA heart failure class and prior heart failure hospitalizations

- Left ventricular ejection fraction (historical values may be used if performed within 24 months of the screening visit, or 36 months if LVEF \leq 30%) must be performed at least 12 weeks after major cardiac intervention-including CABG, valvular intervention, or cardiac resynchronization therapy device implantation
- Blood samples for hematology, iron indices, and NT-proBNP (central laboratory)
- Concomitant medications
- Review inclusion/exclusion criteria
- Enter participant in the Interactive Response Technology (IRT) system to obtain screening number.

Participants who do not meet study entry criteria should be entered into the IRT system as a screen failure.

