Unless otherwise stated, timings of efficacy endpoints will be relative to the date of randomization. Specifically, for all time-to event analyses (defined as [event date – randomization date] +1 where event occurs and as [appropriate censoring date based on analytic population – randomization date] +1 where event does not occur), the treatment groups will be analysed using a Cox proportional hazards model that includes treatment as an explanatory factor, region as stratification factors along with pre-specified baseline covariates: age, sex, ejection fraction, NYHA class, heart failure etiology (Ischemic vs. non-ischemic (unknown etiology considered as non-ischemic)), NT-proBNP, haemoglobin, ferritin, TSAT, eGFR and BMI, unless specified otherwise. If any of the pre-specified baseline covariates have >5 participants with missing data, they will not be used in the analyses to maintain the ITT population for the model. If the baseline covariate is missing data on ≤ 5 participants, we will impute the missing value with overall mode if categorical covariate and the overall mean if continuous variable. The Efron method will be used for handling ties. P-value and confidence intervals for the HR will be based on the Wald statistic. Any analyses using events that are confirmed by the CEC will use the CEC adjudicated responses and related dates. Analyses of Cardiovascular (CV) death, will include deaths with cause of death confirmed as unknown. In addition, the summary tables of these analyses will include the number of participants with event and the cumulative incidence (1 – the “survival” or event-free proportion) over time per treatment group presented annually through the last time point where 90% of the overall events have occurred. Cumulative incidence function and Kaplan-Meier estimates of participants with events will also be calculated and plotted through maximum follow up available in the study, with number of participants at risk indicated below the plot at specific times.

We will present empirical cumulative distribution function curves by treatment of change in 6MWT distance at 6 and 12 months.

For all the hierarchical composite endpoints, in addition to primary analytic method, we will present win-ratio along with its confidence interval.

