5.3.2 FCM vs. Placebo for Top Secondary Outcome

This analysis will compare time from randomization to the first occurrence of CV death or hospitalization for heart failure. The Cox proportional hazards model will be employed to conduct this comparison. The Cox model will include treatment, region as a stratification variable and will be adjusted for pre-decided baseline covariates as noted in section 4.1. The test will be two-tailed and will be performed at an overall α of 0.04. This analysis will be performed by the ITT principle based on randomized treatment assignment and we expect adequate power to detect a pre-specified relative risk reduction of 20%.

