5.4 Subgroup Analyses for Top Secondary Outcome

Subgroup analyses will be performed for the top secondary outcome in the ITT population in order to explore whether treatment effects on the risk of developing CV events are consistent across subgroups. Subgroup analyses will be performed using the same analysis models as for the top secondary endpoints, with the addition of the subgroup factor and its interaction with treatment. The same subgroup analyses will also be repeated in the PP population.

The subgroups will be divided by categories for continuous variables. The subgroup analyses will be summarized via a forest plot and interaction p-values will be reported. We would look further into the subgroup if any interaction p-values are smaller than 0.15. Pre-specified subgroups are detailed below.

Key Subgroups of Interest include split by:

Age (<65 vs ≥65 years old),
NT-proBNP (<median vs ≥median pg/mL),
NYHA class (I and II vs III and IV),
Heart failure etiology (Ischemic, Non-ischemic, Unknown),
Ejection fraction (≤ median vs. > median),
Estimated glomerular filtration rate (<60 vs 60+ ml/min/1.73m²),
Sex (Male/Female),
Ferritin-TSAT (<100 ferritin vs ferritin ≥100-300 with TSAT<20%),
Chronic renal insufficiency (Yes/No),
Diabetes mellitus (Yes/No),
Iron deficiency anaemia (female and haemoglobin <12 g/dL or male and haemoglobin <13.5 g/dL, vs higher haemoglobin value for either sex),
BMI (<25, ≥25 to <30, and ≥30),
Region (North America, Europe (includes Russia and Georgia), Asia Pacific),
Race (White, Black, Other(American indian or Alaska native, Asian, multiple, native Hawaiian or other pacific islander, other)),
Atrial fibrillation (Yes/No),
Hospitalization for HF within past 12 months (Yes/No)

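### The top secondary Cox model omits prior-year HF hospitalization, the other half of inclusion criterion 7, and so leaves a small avoidable attenuation of the treatment effect

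*Combined protocol and SAP*

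**What the plan says.** SAP v1.3, section 4.1, sets the default for time-to-event analyses: a Cox model with treatment, stratified by region, and with "pre-specified baseline covariates: age, sex, ejection fraction, NYHA class, heart failure etiology" followed by "NT-proBNP, haemoglobin, ferritin, TSAT, eGFR and BMI, unless specified otherwise". That makes eleven covariates. Section 5.3.2 applies them to the top secondary outcome, whose model "will be adjusted for pre-decided baseline covariates as noted in section 4.1". HF hospitalization in the past year is not among them, and no reason is given.

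The variable appears in three other places:
- Protocol v3, section 4.2.1, criterion 7 admits participants with "Either documented hospitalization for heart failure within 12 months of enrollment or elevated N-terminal-pro-brain natriuretic peptide".
- Protocol v3, section 6.2.1, has the screening visit record "Demographic and medical history including NYHA heart failure class and prior heart failure hospitalizations".
- SAP v1.3, section 5.4, lists it as a pre-specified subgroup: "Hospitalization for HF within past 12 months (Yes/No".

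Under section 5.4 the subgroup factor and its interaction with treatment are added to the model, so prior hospitalization enters a model only in its own subgroup analysis.

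Section 4.1 also drops any listed covariate that is missing in more than 5 participants. With 5 or fewer missing, it imputes the overall mode or mean.

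**The concern.** Criterion 7 is an either/or rule, and the model carries only one side of it. A participant with a low natriuretic peptide can enter only through a recent HF hospitalization. Among those enrolled, NT-proBNP alone may therefore understate risk in the group that came in by the other route. HF hospitalization is also a component of the top secondary outcome, so a recent one is plausibly prognostic.

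In a Cox model, leaving out a prognostic covariate pulls the conditional treatment log-HR towards zero, even under randomization, because the hazard ratio is non-collapsible. What is at stake is some power on a test with little to spare (see the first step of the check).

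**Working it through.** **1. The plan's own figure.** SAP section 1.4 gives HR 0.80, 1:1 allocation, 771 events and 90% power at overall two-sided alpha 0.05. The final test of the top secondary now uses 0.0399.
- Schoenfeld events for 90% power at 0.05: 4 × (1.960 + 1.282)² / (ln 0.80)² = 845, not 771.
- Power at 771 events: Φ(√(771/4) × 0.2231 − z). This is 87.2% at 0.0499 and 85.2% at 0.0399. At 0.0399, 90% power would need 895 events.
- The count itself fits the plan's accrual assumptions. With s = hazard + 0.0021, the event probability per arm is (hazard/s) × [1 − (e^(−12s) − e^(−42s))/(30s)]. With hazards of 0.0128 and 0.01024 and 1500 per arm, this gives 420 + 348 = 767 events.

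So 771 is reproduced as an expected count, but not as the number needed for 90% power. That mismatch is a separate matter; here it only sets the baseline.

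**2. Inputs for the omission.** From the documents: N = 3000, control rate 0.0128 per month, HR 0.80, 30 months of uniform accrual, loss 0.0021 per month, 771 events, alpha 0.0399. Assumed, because the documents are silent:
- prevalence of prior-year HF hospitalization 35% to 50%;
- its HR given the other covariates 1.3 to 2.0;
- the listed covariates represented by one score with SD 0.6 on the log-hazard scale;
- correlation of 0 or 0.2 between that score and the propensity to prior hospitalization.

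**3. Method.** 600 simulated trials per scenario, each fitted with and without prior hospitalization (HFH). The SE of the treatment log-HR was 0.0724 in both fits in every scenario. Let r be the mean log-HR without the variable divided by the mean with it.
- Power with the variable: Φ(0.2231/0.0724 − 2.055) = 84.8%.
- Power without it: Φ(0.2231 × r/0.0724 − 2.055).
- Equivalent extra events: 771 × (1/r² − 1).

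| Prevalence | HR of HFH | Correlation | log-HR without | log-HR with | r | Power without | Gain (points) | Events |
|---|---|---|---|---|---|---|---|---|
| 35% | 1.3 | 0.2 | −0.2213 | −0.2223 | 0.9955 | 84.5% | 0.33 | 7 |
| 35% | 1.6 | 0.2 | −0.2130 | −0.2153 | 0.9893 | 84.0% | 0.79 | 17 |
| 50% | 1.6 | 0.2 | −0.2252 | −0.2273 | 0.9908 | 84.1% | 0.68 | 14 |
| 35% | 1.6 | 0 | −0.2215 | −0.2236 | 0.9906 | 84.1% | 0.69 | 15 |
| 35% | 2.0 | 0.2 | −0.2196 | −0.2246 | 0.9777 | 83.1% | 1.67 | 36 |
| 50% | 2.0 | 0.2 | −0.2219 | −0.2261 | 0.9814 | 83.4% | 1.39 | 29 |

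Example, fifth row: r = 0.2196/0.2246 = 0.9777. Power without is Φ(0.2231 × 0.9777/0.0724 − 2.055) = Φ(0.959) = 83.1%, a gain of 1.67 points. Events: 771 × (1/0.9777² − 1) = 36.

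The ratio is taken within the same simulated trials because directly counted rejection rates are too coarse: with 600 runs near 84%, each has a standard error of √(0.84 × 0.16/600) = 1.5 points.

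**4. Scale and cross-check.** In the same simulations, the score standing for the listed covariates raised power by about 3 to 5 points over the unadjusted model, so most of the benefit of adjustment is already in the plan. A separate simulation imposed the either/or entry rule (assumed 44% prevalence, score SD 0.5, 200 runs). Adding prior hospitalization alone gained 0.4, 1.4 and 0.4 points for NT-proBNP/hospitalization HRs of 1.35/1.35, 1.5/1.8 and 1.8/1.35. These fall within the range above.

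**The case against.** The case for leaving the model alone is respectable. Eleven pre-specified covariates with stratification by region is a sound analysis. The list was added in SAP v1.1, and v1.2 followed with changes after FDA feedback. Diabetes and atrial fibrillation are also subgroups and not covariates, and being a subgroup does not oblige adjustment. Correlated markers such as NT-proBNP and NYHA class are already in. The gain is under one point unless the HR is near 2.0 after adjustment, and every input that drives it is assumed. The variable may also prove incomplete and be dropped under the section 4.1 rule.

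All of that stands, and it limits the point to a small efficiency gain. It does not remove the point: unlike the other unadjusted subgroup factors, this one decides eligibility and is a past instance of an outcome component, and adding it costs one parameter.

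A reader might infer more than the documents support:
- **Lost precision.** The SE is the same with and without the variable. The gain comes only from removing attenuation.
- **Bias or inflated type I error.** Randomization protects the test under the null. Poorer risk prediction in the hospitalization-only group does not bias the comparison of arms.
- **Wrong scale for NT-proBNP and ferritin.** Section 4.1 names variables and states no functional form, and the introduction defers definitions to a supplemental appendix. The documents report no skewness, and criterion 6 caps ferritin at 300 ng/mL at entry.
- **Harmful mean imputation.** The rule covers at most 5 participants per covariate.

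**Conclusion.** The point holds as a minor missed efficiency gain. The model includes one side of criterion 7 and omits the other, although the omitted variable is collected and already named in the SAP. The cost is an attenuation of the conditional log-HR of about 0.5% to 2%, or about 0.3 to 1.7 points of power (roughly 7 to 36 events' worth) at 771 events and alpha 0.0399.

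The range rests on the assumed prevalence and prognostic strength. The upper end needs an HR of 2.0 given the other covariates; at HR 1.6 the gain is 0.7 to 0.8 points. The analysis as planned remains valid. The gain is worth taking because power at the final alpha is already near 85%.

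**What to change.** Before unblinding, add 'HF hospitalization within 12 months before enrollment (yes/no)' to the section 4.1 covariates for the top secondary Cox model, derived as for the section 5.4 subgroup and subject to the existing missing-data rule. If it is deliberately left out, record why.

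Section 5.5 analyses the other time-to-event secondary outcomes by the same approach as the top secondary, so the new text should say whether the addition carries over to them. The gain was computed only for the top secondary.

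The cost is one line of SAP text and one model parameter, with no new data collection. SAP v1.3 states that all its changes were made before unblinding; this change must meet the same condition.

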6.3 Treatment Phase (Day 0 to Day 7)

6.3.1 Day 0 Visit

All eligible participants will be randomized to either Group A or Group B in a 1:1 ratio based on a pre-determined randomization schedule via an IRT system.

The following will be obtained and/or completed before contacting IRT for randomization:

For all participants (all procedures to be performed by blinded study personnel):

- Verify all inclusion and exclusion criteria
- Height and weight
- Targeted physical exam
- Blood samples for central lab hematology, chemistries and iron indices for all participants; For Hypophosphatemia Sub-Study participants only: 1,25 (OH)₂ Vitamin D, 25 (OH) Vitamin D and PTH.
- Review concomitant medications
- Urine or serum pregnancy test (women of childbearing potential only)
- Administer 6MWT per standardized procedure

The IRT system will then be contacted by an **Unblinded** study team member and all eligible participants will be randomized to either Group A or Group B in a 1:1 ratio with stratification by region based on a pre-determined randomization schedule. After assignment of the treatment group the following will occur:

Note: To avoid unblinding on the dose administration worksheet, if a participant is under 50 kg, the volume of FCM or placebo administered should be calculated based on the participant's weight, e.g. a 45 kg participant will receive a 13.5 mL dose of FCM or placebo.

Note: All IV injection start and stop times should be captured in hh:mm:ss format.

Group A:

- Verify amount of single FCM dose (15 mg/kg up to a maximum dose of 750 mg) (unblinded staff)

- Pre-administration, obtain heart rate, blood pressure, and body temperature (blinded staff)
- Administer FCM as a slow IV injection at the rate of approximately 2 mL /minute taking appropriate measures to ensure the participant and all blinded staff members remain blinded to the treatment being administered (unblinded staff).
- Document start and stop time of FCM administration and the total dose and volume administered (unblinded staff)
- Post-administration, obtain heart rate and blood pressure immediately after and 30 minutes after FCM administration (blinded staff). Participants will be discharged from the site by the Investigator or his or her designee only if there are no significant signs or symptoms 30 minutes after the administration is completed.
- Adverse event / serious adverse event assessment (starting at beginning of FCM injection) (blinded staff)

Group B:

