8.7 Secondary Comparisons

8.7.1 Top Secondary Comparison: Time to first event of cardiovascular death or hospitalization of heart failure

This analysis will compare time to first occurrence of cardiovascular death or hospitalization for heart failure. The Cox proportional hazards model will be employed to conduct this comparison. The test will be two-tailed and will be performed at an overall α of 0.05. This analysis will be performed by the ITT principle based on randomized treatment assignment and we expect adequate power to detect a pre-specified relative risk reduction of 20%.

Sensitivity Analysis

In a sensitivity analysis we will add another layer to the hierarchy described above – in individuals who have been hospitalized for heart failure during follow-up, ties in the numbers of hospitalizations will be resolved based on the total number of days in the hospital during follow-up, before proceeding to comparison of differences in the 6MWT.

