1.4 Sample Size and Power

The study design allows for sufficient power for both the primary and top secondary outcomes. Numerical simulations based on multivariate normal vectors ([Appendix 2](#)) were conducted to estimate power for the primary treatment comparison based on the following assumptions about events rates described in **Table 1.4.1**

Table 1.4.1. Assumptions about Event Rates for Primary Outcome

Ranked tier at 12-month endpoint (6 month for 6 MWT)	Control	Treatment
Death total	8%	6.8%
Death without hospitalization	4%	3.4%
Death with hospitalization	4%	3.4%
Hospitalizations in survivors		
1	6%	4.8%
2	3%	2.4%
3 or more	1%	0.8%
Change in 6 Minute Walk Test	Mean = 0 SD = 90	Mean = 18 SD = 90

With 3014 participants (1507 per arm) and 2.5% annual loss to follow-up for clinical outcomes and 15% of individuals with missing 6MWT at 6 months (unable to perform or lost to follow-up), projected simulations estimate 90% power at an overall two-sided significance level of 0.01, accounting for one interim analysis as described in [Section 7.1](#).

For the top secondary composite, there is an assumed event rate of 0.0128 per month in the control arm which represents conservative 75% discounting of the event rate obtained by the FCM meta-analysis [[Anker 2015](#)]. The anticipated hazard ratio (HR) was set at 0.80 (20% reduction). Uniform enrollment was assumed over the period of 30 months, with an anticipated minimum follow-up of 12 months (required minimum of 6 months), anticipated maximum follow-up of 42 months (no required maximum), and monthly loss to follow-up of 0.0021 (2.5% annualized). With these assumptions, 1500 per study arm (3000 total) provides 90% power to reject the null hypothesis of no difference between treatment arms when tested at an overall two-sided level of significance $\alpha=0.05$, accounting for one interim analysis as described in Section 8.10 of the CSP. This results in a total of 771 participants with events (in case of multiple events experienced by a participant, only their first one will be counted towards the 771) necessary to achieve the desired power. Thus, the trial has the potential opportunity to be stopped at a point where the projected number of participants reaches 771 events, but no earlier than the last participant reaching 12 months of follow-up.

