4.4 Handling of Missing Data

4.4.1 Outcome Data/Dates

The primary analysis will rely on a multiple imputation model, with Markov chain Monte Carlo algorithm based on the totality of observed data. One exception to this rule will be that

individuals unable to perform the 6MWT test at 6 months i.e. those who did not perform a 6MWT or died prior to 180 days will have their value imputed as the worst possible 6MWT distance which is 0 meters. Any missing death dates will be imputed using date imputation rules in this section. A baseline 6MWT distance is needed to be able to calculate change from baseline 6MWT, hence, any missing baseline 6MWT distance will be imputed as overall mean to allow full ITT population to be included in primary analyses.

The SAS PROC MI procedure will be used for multiple imputations on the 6 month 6MWT distance, with 20 imputations. To ensure consistency in the imputed data for future possible validations, a seed number will be fixed to 1000. Baseline 6MWT, treatment and region will be included as covariates in the imputation model. We will include all observed data in the imputation model with the exception of participants unable to perform 6MWT at 6 months who will have their 6MWT distance included as 0 meters before performing multiple imputation. Imputed data set(s) will include an index variable to identify the number of imputed data. The results across the imputed datasets will be combined using Rubin's rule ([Rubin 1987](#)) to obtain one set of results for the primary analysis. These same missing data handling rules will be used for the Win-Ratio analyses. Basic statistics on the overall original data (incomplete data) and the data following imputation will be provided in the Clinical Study Report (CSR).

For secondary efficacy endpoints, missing data relating to the indicator for the confirmed composite CV outcome and/or its components will not be imputed. Any partial or completely missing date for a confirmed composite CV outcome at the time of database lock will be imputed as follows:

- If the day is missing, 15th of the month, or the randomization date (if participant randomized after 15th of the same month and same year) will be used, making sure the imputed date is not post date last known alive on end of study form;

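### SAP 4.1 drops a pre-specified Cox covariate once six participants lack a value, although the mean/mode imputation it already prescribes would keep the full ITT set at any count

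*Combined protocol and SAP*

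**What the plan says.** SAP v1.3, section 4.1, sets the Cox model for time-to-event analyses: treatment, region as stratification factor, and 11 baseline covariates (age, sex, ejection fraction, NYHA class, aetiology, NT-proBNP, haemoglobin, ferritin, TSAT, eGFR, BMI). Two rules for missing covariate values follow.

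- Six or more missing: "If any of the pre-specified baseline covariates have >5 participants with missing data, they will not be used in the analyses". The reason given is to keep the ITT population in the model.
- Five or fewer missing: "we will impute the missing value with overall mode if categorical covariate and the overall mean if continuous variable".

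Section 5.3.2 applies this set to the top secondary outcome, which "will be adjusted for pre-decided baseline covariates as noted in section 4.1". Section 5.5 extends the approach to the other time-to-event secondary outcomes. Section 5.4 carries it into the subgroups: "Subgroup analyses will be performed using the same analysis models as for the top secondary endpoints".

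For the primary endpoint, section 4.4.1 handles a missing baseline walk distance without any count limit: "any missing baseline 6MWT distance will be imputed as overall mean to allow full ITT population to be included in primary analyses".

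**The concern.** The only reason given for removal is preservation of the ITT set, and the imputation rule in the next sentence already achieves that at any count. Dropping a covariate is equivalent to giving all 3014 participants the same value, since a constant contributes nothing to a Cox model. Imputation does this only for the few whose value is missing. No reason is given for the number five.

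The adjustment set of the top secondary test, which section 5.3.2 treats as decided in advance, can therefore depend on whether five or six values are missing. Because hazard ratios are non-collapsible, a different set also means a slightly different conditional hazard ratio is being estimated. What is at stake is precision. The rule is pre-specified and uses a pooled count that can be read blinded, so it does not threaten type I error.

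**Working it through.** **Inputs from the documents.** N = 3014; HR 0.80; 771 events; control rate 0.0128 per month; 30 months of uniform accrual, 12 to 42 months of follow-up; loss 0.0021 per month; final two-sided alpha 0.0399 for the top secondary (all SAP 1.4).

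**Assumptions.** Missing rate, hazard ratio per SD of the covariate, and its R² with the retained covariate. The documents give none of these.

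**1. The plan's power figure.** There is no document figure for the missing-value rule itself. SAP 1.4 says: "With these assumptions, 1500 per study arm (3000 total) provides 90% power". The Schoenfeld formula gives power = Φ(√D/2 × |ln HR| − z). With D = 771 and HR 0.80 the first term is 27.77/2 × 0.2231 = 3.098.

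- Alpha 0.0499: Φ(3.098 − 1.961) = 87.2%.
- Alpha 0.0399: Φ(3.098 − 2.055) = 85.2%.

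By this formula, 90% power at 0.05 needs 845 events. The gap from the stated 90% is a separate matter. The 85.2% is used below only as the no-covariate reference. The plan assumed no covariates: Protocol 8.7.1 says "The Cox proportional hazards model will be employed to conduct this comparison" and names none.

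**2. How low the threshold is.** 5/3014 = 0.17%. Removal starts at 6/3014 = 0.20%. The chance that a given covariate is removed is P(X > 5), X ~ Bin(3014, p):

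| Assumed missing rate | Chance of removal |
|---|---|
| 0.05% | 0.5% |
| 0.1% | 8.5% |
| 0.15% | 30% |
| 0.2% | 56% |
| 0.3% | 89% |

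**3. Does imputation keep the ITT set?** Yes. The overall mean or mode fills every gap, so 3014 of 3014 remain in the model whether 5, 6, 30 or 150 values are missing.

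**4. What removal costs.** Cox simulation with the inputs above (4000 replicates, about 763 to 772 events): one retained covariate (log-HR 0.3 per SD) plus the covariate at issue, and the treatment effect set so that the unadjusted HR is 0.80. Power is taken from the mean Z, scaled so that the no-covariate model equals 85.2%.

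| HR per SD | R² | Removed | Kept | Loss (points) |
|---|---|---|---|---|
| 1.25 | 0 | 86.1% | 86.6% | 0.56 |
| 1.5 | 0 | 86.0% | 87.8% | 1.84 |
| 1.75 | 0 | 86.0% | 89.4% | 3.41 |
| 1.25 | 0.5 | 87.3% | 87.6% | 0.28 |
| 1.5 | 0.5 | 88.6% | 89.6% | 0.96 |
| 1.75 | 0.5 | 89.8% | 91.5% | 1.77 |

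Losses are computed before rounding. A smaller simulation (500 replicates, Monte Carlo SE about 1.7 points) instead set the conditional HR at 0.80 and had no retained covariate. It gave larger losses: about 1 to 2 points at a log-hazard SD of 0.4, 5 to 6 at 0.6 and 5 to 11 at 0.8. On that scale omission also attenuates the unadjusted HR, to about 0.80 to 0.82. The table is closer to the plan, whose 0.80 belongs to a model without covariates.

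**5. Imputation against removal.** HR 1.75 per SD, R² 0, 2500 replicates, unscaled: removed 84.7%, complete data 88.3%. Pooled mean imputation gave 88.3%, 88.2% and 88.0% with 1%, 5% and 10% missing at random, and 87.8%, 87.5% and 86.9% with 5%, 10% and 20% missing not at random. At HR 1.5 and R² 0.5: removed 88.1%, complete 89.1%, imputed with 20% missing not at random 88.5%.

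**6. Type I error at HR 1.0** (nominal 0.0399, SE 0.003): removed 0.040, complete 0.042, imputed 0.038 to 0.043.

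**The case against.** The rule meets its stated aim: it is fixed in advance, uses pooled counts and keeps the ITT set. On this view, choosing between two valid ITT-preserving rules is a preference, and any threshold turns on one observation. That is right as far as validity goes, but the SAP gives no advantage of removal to set against the lost precision.

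The baseline walk distance in section 4.4.1 is not a like-for-like precedent. It is needed to compute the endpoint and cannot be dropped, whereas a covariate can. This stands, and the case does not depend on the comparison.

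Missing values may be rare. Unknown aetiology is already coded as non-ischaemic. Several covariates are needed for eligibility. Haemoglobin, iron indices and NT-proBNP are scheduled at both screening and Day 0, so a screening value can serve as baseline. By the schedule only eGFR and BMI have a single pre-dose measurement, and the height, weight and chemistries behind them come under Protocol 6.3.1: "The following will be obtained and/or completed before contacting IRT for randomization". This also stands: nothing shows that six values will be missing for any covariate. Against it, SAP 4.1 itself anticipates missing baseline values and names central laboratory measures as its example.

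The loss may be smaller than tabulated, since the real model would retain ten covariates. A rough check with three retained covariates (200 replicates) gave 0.2 to 0.8 points at R² 0.7, and 0.1 to 1.5 points for a right-skewed, untransformed covariate. Removal still lost a little each time.

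Unlimited imputation might seem to go beyond the tested range. A further simulation (400 replicates per case) covered a mode-imputed binary covariate with 30% missing not at random and a mean-imputed continuous one with 40%. Imputation still gave slightly more power than removal.

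**Conclusion.** The concern holds at low priority. Removing a covariate at six missing values is unnecessary for the purpose the SAP states, and the cut-off of five is unexplained. The cost is efficiency only, about 0.3 to 3.4 power points per removed covariate on the planned scale and probably towards the lower end if the retained covariates are correlated with it. After removal, power in the tabulated cases is 86.0% to 89.8%, above the 85.2% no-covariate reference, so the trial loses part of a gain the sample size never counted on. Type I error and the primary test are untouched. Missing rates, prognostic strengths and correlations are all assumed. The direction, imputation at least as good as removal, was the same in every case tested.

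**What to change.** In SAP section 4.1, delete the sentence that removes covariates and the five-or-fewer condition on imputation. Replace both with:

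> *All 11 pre-specified covariates are kept in the model. Missing baseline values are imputed with the overall mode (categorical) or overall mean (continuous), pooled over treatment arms, whatever the number missing.*

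This fixes the adjustment set in advance for the top secondary, other time-to-event and subgroup models. It needs no new data, only a new SAP version before unblinding with the Steering Committee approval that Protocol 10.1 requires. Because version 1.2 changed the top secondary analysis after FDA feedback, a further regulatory exchange is possible; the change is best bundled with any other SAP revision.
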